11.3 Case Report Forms

The study case report form (CRF) will be the primary data collection instrument for the study. All data requested on the CRF will be recorded. All missing data will be explained. If a space on the CRF is left blank because the procedure was not done or the question was not asked, "N/D" will be written. If the item is not applicable to the individual case, "N/A" will be written. All entries will be printed legibly in black ink. If any entry error has been made, to correct such an error, a single straight line will be drawn

H-39712: Peer Recovery Coaching for Infectious Diseases and Opioid Use Disorder
Version 1.1 07/07/2020

through the incorrect entry and the correct data will be entered above it. All such changes will be initialed and dated. There will be no erasures or white-out on CRFs. For clarification of illegible or uncertain entries, the clarification will be printed above the item, then initialed and dated. The following source data will be recorded directly on the CRFs: [data where the CRF will be the source document](#).

See the Appendix for the following CRFs: [list one or more CRF by name](#)

11.4 Study Records Retention

Records will be maintained for seven years after the research is completed.

12 Statistical Plan

12.1 Study Hypotheses

The goal of the current proposal is to determine the feasibility and acceptability of a peer recovery coaching (PRC) intervention to improve infectious diseases (HIV/HCV) prevention and care alongside treatment for opioid use disorder.

Aim 1: To implement a pilot peer recovery coaching intervention at a walk-in low-barrier bridge clinic to increase uptake of a comprehensive intervention for HIV PrEP, HCV and substance use treatment among PWID accessing care at BMC FASTER PATHS bridge clinic

Aim 2: To determine the feasibility and acceptability of a combined PrEP, HCV and substance use treatment intervention at the BMC FASTER PATHS bridge clinic.

We hypothesize that the peer recovery coaching intervention will facilitate both access to PrEP, HCV treatment and sustained engagement with treatment for opioid use disorder among participants. The primary outcome is patient satisfaction as a measure of the intervention's acceptability. Secondary outcomes will include (1) the proportion of patients with linkage to PrEP and treatment initiation within 3 months; (2) the proportion of patients with HCV treatment initiation within 3 months; (3) the proportion of patients with sustained linkage to opioid use treatment within 3 months (follow-up with at least one subsequent visit after the initial prescription for medication for opioid use disorder).

12.2 Sample Size Determination

H-39712: Peer Recovery Coaching for Infectious Diseases and Opioid Use Disorder
Version 1.1 07/07/2020

Given the small sample size, we are not powered to show efficacy, but we will use findings to estimate the effect size for a future efficacy trial.

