Intervention:	Peer recovery coaching (PRC) to improve linkage to HIV prevention in the form of HIV pre-exposure prophylaxis (PrEP) and hepatitis C (HCV) treatment.
Objectives:	Our goal is to determine if a peer recovery coaching intervention will help patients initiate HIV prevention in the form of HIV pre-exposure prophylaxis (PrEP), HCV treatment and substance use disorder (SUD) treatment.
Design/Methodology:	Participants who consent will work one-on-one with a peer recovery coach who will provide support and linkage to various HIV, HCV and SUD resources.
Total Study Duration:	Time from initial enrollment until completion of data analysis= 12 months
Subject Participation Duration:	Time it will take to conduct the study for each individual participant =6 months

3 Background/Rationale & Purpose

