4.1.2 Secondary Outcome Measures

Secondary outcomes will include the following:

- (1) The proportion of participants with linkage to care.
- (2) The proportion of participants retained in care
- (3) The following additional outcomes:

HIV PrEP-related outcomes: Testing for sexually transmitted diseases including HIV, gonorrhea, chlamydia, syphilis, and hepatitis B and C.

HCV continuum of care outcomes: HCV RNA testing, liver fibrosis staging, treatment initiation and cure.

Opioid use disorder treatment-related outcomes: The proportion of individuals with repeat MOUD clinic visits and/or repeat prescriptions for opioid use disorder including buprenorphine and naltrexone, or linked to methadone treatment.

5 Study Design

The study is prospective open pilot study (N=40).

We will include 40 persons with a history of substance use recruited from the BMC FASTER PATHS bridge clinic, a facility caring for approximately 500 unique patients annually. The BMC FASTER PATHS bridge clinic provides universal HIV and HCV testing at the initial clinic intake. After reactive HCV testing, patients are linked to care at the BMC General Internal Medicine (GIM) primary care clinic.

The goal of the current study is to determine feasibility and acceptability of a peer recovery coaching intervention to improve the uptake of HIV prevention, HCV treatment

H-39712: Peer Recovery Coaching for Infectious Diseases and Opioid Use Disorder
Version 1.1 07/07/2020

and substance use treatment at a low-barrier bridge clinic. Along with the research assistant, the peer recovery coach is part of the research staff. The peer recovery coach will carry out the intervention (ie. use motivational interviewing to help participants address their history of opioid use while also accessing treatment for hepatitis C and HIV prevention methods). The peer recovery coach will carry out a baseline motivational interviewing intervention with participants and they will continue to follow the participants over a 6-month time frame. Frequency of follow-up calls will vary depending on the participant's need. The recovery coach will initially start with weekly calls.

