12.3 Statistical Methods

Primary outcome will include patient satisfaction as a measure of the PRC intervention's acceptability.

Qualitative semi-structured interviews will be audio recorded, professionally transcribed and analyzed using NVivo computer software. We will develop a codebook to determine acceptability and feasibility of the intervention, apply codes to all transcripts and analyze the data to identify emerging themes. We will also use descriptive statistics to summarize findings, and the Wilcoxon test to compare 5-point Likert scales between the two groups. For the secondary outcome, we will use descriptive statistics without hypothesis testing to compare outcomes in the intervention group to the current practice group. We will compare the two groups on demographic characteristics (age and gender), linkage to care, loss to follow-up and other secondary outcomes.

13 Ethics/Protection of Human Subjects

This study is to be conducted according to applicable US federal regulations and institutional policies (which are based in federal regulations, guidance, and ICH Good Clinical Practice guidelines).

This protocol and any amendments will be submitted to the Boston Medical Center and Boston University Medical Campus IRB, for formal approval of the study conduct. The decision of the IRB concerning the conduct of the study will be made in writing to the investigator.

All participants for this study will be provided a consent form describing this study and providing sufficient information for subjects to make an informed decision about their participation in this study. The consent form will be submitted with the protocol for review and approval by the IRB. The consent of a subject, using the IRB-approved consent form, must be obtained before that subject is submitted to any study procedure. Consent will be documented as required by the IRB.

14 Literature References

H-39712: Peer Recovery Coaching for Infectious Diseases and Opioid Use Disorder
Version 1.1 07/07/2020

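### Section 12.2 promises an effect size for a future efficacy trial, but one coached cohort of 40, or about 20 per group, cannot give a usable one

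*Combined protocol and SAP*

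**What the plan says.** Section 5 (Study Design) gives the sample size without a derivation: "The study is prospective open pilot study (N=40"). Section 12.2 (Sample Size Determination) concedes that "we are not powered to show efficacy" and then states the use to be made of the data: "we will use findings to estimate the effect size for a future efficacy trial". It names no outcome for that effect size, no precision target and no safeguard.

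The documents differ on whether there is anything to compare. The synopsis says "Participants who consent will work one-on-one with a peer recovery coach". Sections 5, 7 and 8 describe one recruitment stream, one set of eligibility criteria and one intervention, with no allocation. Section 12.3, however, plans "the Wilcoxon test to compare 5-point Likert scales between the two groups", and for the secondary outcome says "we will use descriptive statistics without hypothesis testing to compare outcomes in the intervention group to the current practice group". The source, size and timing of that second group are not given anywhere.

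The natural candidates for an effect size are the 3-month binary outcomes in sections 4.1 and 12.1, for example "the proportion of patients with HCV treatment initiation within 3 months". Section 12.3 does not call for confidence intervals.

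**The concern.** An effect size for an efficacy trial is a contrast between coached and uncoached people. A cohort in which everyone is coached does not contain that contrast. If 40 people are split, the contrast exists but is very imprecise.

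Conceding that the study cannot test efficacy does not cover this second use, because the imprecision that rules out a test also limits the estimate as a planning value. The sentence stands under the sample size heading, and that section gives no other use for the 40 participants. Whoever plans the next trial could therefore take the pilot figure at face value and carry its sampling error into that trial's size and power.

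**Working it through.** **Plan's own figure.** N=40 comes with no alpha, power, rates, effect or precision target, so there is no calculation to reproduce.

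**Inputs.** From the documents: 40 participants and binary outcomes at 3 months. Assumed, because the documents are silent: a usual-care rate of 20%, a coached rate of 40% or 35%, a future trial with two-sided 5% alpha and 80% power, and no dropout except where 32 evaluable (20% loss) is shown.

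**Step 1: one cohort of 40.** Only a rate can be estimated. The Wilson 95% interval is [p + z²/2n ± z√(p(1−p)/n + z²/4n²)] / (1 + z²/n), with z = 1.96.
- 16/40: centre (0.4 + 0.0480)/1.0960 = 0.409; half-width (1.96/1.0960) × √(0.0060 + 0.0006) = 0.145; interval 26.3% to 55.4%.
- Worst case, 20/40: 35.2% to 64.8%, half-width 14.8 points.
- 16/32: 33.6% to 66.4%, half-width 16.4 points.

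**Step 2: 20 against 20.** The half-width of a difference at 40% against 20% is 1.96 × √(0.4×0.6/20 + 0.2×0.8/20) = 1.96 × √0.020 = 0.277, about 28 points around a 20-point effect. The Newcombe interval for 8/20 against 4/20 runs from −8 to +45 points.

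**Step 3: what one pilot result implies for the next trial.** With d the difference and p̄ the mean rate, n per arm = [1.96√(2p̄(1−p̄)) + 0.842√(p₁(1−p₁) + p₂(1−p₂))]² / d².
- 40% against 20%: (1.270 + 0.532)² / 0.04 = 81.2, so 82 per arm.
- At the Wilson limits of 16/40 (26.3% and 55.4%) against 20%: 693 and 29 per arm.
- 35% against 20%: 138 per arm.

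**Step 4: true power if the raw estimate is used.** Each possible pilot result is put through the formula above. The resulting n is then evaluated at the true rates: power = Φ{[d − 1.96√(2p̄(1−p̄)/n)] / √[(p₁(1−p₁) + p₂(1−p₂))/n]}.

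Example: the truth is 35% against 20% and the pilot shows 17/40. The trial is sized at 66 per arm, and its true power is Φ[(0.150 − 0.152)/0.077] = 49%. Every result of 17/40 or more does the same or worse, and P(X ≥ 17 | 40, 0.35) = 20.2%. If the truth is 40% against 20%, the threshold is 20/40 (39 per arm), and P(X ≥ 20 | 40, 0.40) = 13.0%.

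Enumerating all results, as a share of all pilots:

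| Design assumed | True rates | Next trial's true power below 50% | No positive effect seen |
|---|---|---|---|
| 40 coached, control rate known exactly | 40% v 20% | 13% | 0.6% |
| 40 coached, control rate known exactly | 35% v 20% | 20% | 3% |
| 20 v 20 | 40% v 20% | 29% | 11% |
| 20 v 20 | 35% v 20% | 33% | 18% |

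**Step 5: sensitivity.** Simulating 20,000 pilots for each of four control and coached pairs (10/25, 20/40, 30/50 and 50/70%), true power falls below 50% in 10% to 13% of all pilots with a known control rate, 21% to 23% with 40 against 40, and 29% to 35% with 20 against 20.

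The error also runs the other way. If the truth is 35% against 20%, an observed 12/40 against the known 20% gives 294 per arm where 138 are needed.

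**The case against.** The plan does not say that the unadjusted point estimate will be the planning effect, or that an interval, a conservative limit or outside data will be ignored. Every power figure above assumes that naive use. Section 12.2 claims no precision and openly concedes the small sample. The stated goal is feasibility and acceptability, with satisfaction as the primary outcome, and any later trial would need its own justification. All of this stands, and it limits the point to wording.

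Three stronger readings are tempting and should be resisted.

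- **That the next trial would often be badly underpowered.** The documents do not commit to the step that produces this. Even granting it, the risk varies about threefold with the group split, which the documents leave undefined.
- **That the share of future trials below 80% power measures the damage.** With 40 coached, a known control rate and 35% against 20%, that share is about 43%. It is about 48% even with a 400-person pilot. Sizing at 80% on any roughly unbiased estimate misses 80% nearly half the time, so the figure says nothing about 40 in particular. Only the lower tail does.
- **That 40 is the wrong sample size for this study.** Nothing in the documents or the calculations shows this for feasibility and acceptability.

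What the objection does not remove is that a single coached cohort contains no between-group effect, and that neither 12.2 nor 12.3 gives a precision statement or an interval to warn a later planner.

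**Conclusion.** The point holds in a limited form. Section 12.2 assigns the data a purpose that the described design cannot meet. On the synopsis and section 5 there is no between-group effect to estimate. On a two-group reading with about 20 each, the half-width of about 28 points exceeds the assumed 20-point effect.

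If the raw estimate were used for sizing, the chance of a trial with less than 50% true power would be about 13% to 20% in the more favourable case and about 29% to 33% with 20 against 20. In the latter case a further 11% to 18% of pilots would show no positive effect. The favourable case needs a control rate known without error, which the documents do not supply. How serious the problem is therefore depends on what section 12.3 means by its second group.

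All rates, the alpha and the power are assumptions. The pilot's own aims and conduct are unaffected, but the stated purpose should be corrected before the results are used for planning.

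**What to change.** In section 12.2, replace the effect-size clause with wording such as: With 40 participants, each proportion will be estimated with a Wilson 95% interval of half-width up to about 15 points (about 16 if 32 are evaluable). The pilot will inform event rates, follow-up and variability for a future trial; its point estimate will not by itself set that trial's target difference.

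In section 12.3, report every proportion, and any between-group difference, with a 95% interval. Reconcile the two-group wording with the single cohort in section 5: either define the comparison group (source, size and timing) or remove the comparison.

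The cost is a few sentences and a less ambitious stated purpose. If the comparison is removed, no new data or participants are needed. If it is kept, the protocol must say where those data come from.

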12.3 Statistical Methods

Primary outcome will include patient satisfaction as a measure of the PRC intervention's acceptability.

Qualitative semi-structured interviews will be audio recorded, professionally transcribed and analyzed using NVivo computer software. We will develop a codebook to determine acceptability and feasibility of the intervention, apply codes to all transcripts and analyze the data to identify emerging themes. We will also use descriptive statistics to summarize findings, and the Wilcoxon test to compare 5-point Likert scales between the two groups. For the secondary outcome, we will use descriptive statistics without hypothesis testing to compare outcomes in the intervention group to the current practice group. We will compare the two groups on demographic characteristics (age and gender), linkage to care, loss to follow-up and other secondary outcomes.

13 Ethics/Protection of Human Subjects

This study is to be conducted according to applicable US federal regulations and institutional policies (which are based in federal regulations, guidance, and ICH Good Clinical Practice guidelines).

This protocol and any amendments will be submitted to the Boston Medical Center and Boston University Medical Campus IRB, for formal approval of the study conduct. The decision of the IRB concerning the conduct of the study will be made in writing to the investigator.

All participants for this study will be provided a consent form describing this study and providing sufficient information for subjects to make an informed decision about their participation in this study. The consent form will be submitted with the protocol for review and approval by the IRB. The consent of a subject, using the IRB-approved consent form, must be obtained before that subject is submitted to any study procedure. Consent will be documented as required by the IRB.

14 Literature References

H-39712: Peer Recovery Coaching for Infectious Diseases and Opioid Use Disorder
Version 1.1 07/07/2020

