4.1.1 Primary Outcome Measures

This is an open pilot study. The Primary outcome will include patient satisfaction as a measure of the peer recovery coach intervention's acceptability.

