7.2 Subject Exclusion Criteria

An individual who meets any of the following criteria will be excluded from participation in this study:

- Individuals unable to provide informed consent
- Unable to speak English
- Individuals already linked to substance use care
- Individuals co-infected with HIV and HCV and engaged in care.

8 Study Intervention

- The intervention: The peer recovery coach with lived experience with recovery from substance use will deliver a semi-scripted brief motivational interview at the time of enrollment. The intervention will last approximately

H-39712: Peer Recovery Coaching for Infectious Diseases and Opioid Use Disorder
Version 1.1 07/07/2020

20 minutes and will take place at the time of the clinical visit while participants are waiting to be seen by a clinician or are awaiting laboratory testing. The intervention will involve the following elements: establishing rapport, asking permission to discuss drugs, discussing the pros and cons associated with drug use, uncovering the gaps between current and desired quality of life and determining readiness to change. Participants will also receive a telephone booster call 5 days following enrollment. The RA will assemble detailed contact information for the patient and will record addresses of two family members or friends. The RA will also collect demographic information and reasons for refusal from individuals who do not participate in the study. Patients seen at the BMC FASTER PATHS bridge clinics usually follow-up at the general medicine clinics at BMC. Following the initial brief motivational interview, the peer recovery coach will remain in contact with participants by phone or in person at least once a week over the following 6-month period and help with facilitating linkage to HIV pre-exposure prophylaxis, HCV and substance use care and treatment.

9 Study Procedures

- The study will be conducted at the low-barrier walk-in clinic at BMC. The clinic sees approximately 500 unique patients annually. After reactive HCV testing at the BMC LBA walk-in clinic, all participants will be linked to care at the BMC General Internal Medicine (GIM) clinic. Participants will be followed for 6 months.
- Recruitment: Participants will be recruited through flyers posted at the LBA walk-in clinic and brief information provided at intake.
 - Flyers advertising the study will be placed in the waiting and common areas of the BMC LBA clinic.

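### Section 12.3 plans two-group analyses against a current practice group, but the study described is a single coached cohort of 40, so those analyses cannot be run as written and the effect size in 12.2 has no comparator.

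*Combined protocol and SAP*

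**What the plan says.** **Design.** The synopsis states that "Participants who consent will work one-on-one with a peer recovery coach". Section 4.1.1 says "This is an open pilot study", and section 5 gives N = 40, all recruited from one bridge clinic. In section 8 the coach "will deliver a semi-scripted brief motivational interview at the time of enrollment" and then stays in contact over six months. No arm, allocation, randomisation, or concurrent or historical control is described.

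**Analysis.** Section 12.3 relies on a second group in three places:
- under the primary outcome, it plans "the Wilcoxon test to compare 5-point Likert scales between the two groups";
- it then turns to secondary endpoints, where the text reads "we will use descriptive statistics without hypothesis testing to compare outcomes in the intervention group to the current practice group";
- a closing sentence widens this to baseline and follow-up variables: "We will compare the two groups on demographic characteristics (age and gender), linkage to care, loss to follow-up and other secondary outcomes".

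**Purpose of the estimate.** Section 12.2 says "we are not powered to show efficacy, but we will use findings to estimate the effect size for a future efficacy trial". It does not say which effect measure or which contrast is meant.

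**The concern.** A between-group comparison needs a second group with the same outcomes measured on it. The current practice group appears only in section 12.3. The analyst would either leave most of the quantitative plan undone or have to find a comparator, possibly after outcomes are known.

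The effect-size aim raises the larger problem. Usual care at this clinic is active: section 3.1 says the clinic links patients to addiction treatment, and section 5 says patients with a reactive HCV test are linked to primary care. A rate observed under coaching therefore includes whatever usual care would have achieved. Carried forward as an effect, it credits coaching with that share, and the next trial is sized on a contrast this study never measured.

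**Working it through.** **1. The plan's own figure.** N = 40 comes with no alpha, power, rate, standard deviation, dropout or allocation ratio, so there is no calculation to reproduce.

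**2. What each 12.3 analysis needs, against what is collected.**

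| Analysis in 12.3 | Needed from a second group | Planned for people not coached |
|---|---|---|
| Wilcoxon on 5-point Likert scales | Likert scores | None |
| Linkage and other secondary outcomes | Record or interview outcomes | None |
| Loss to follow-up | Follow-up contact | None |
| Age and gender | Demographics | Demographics of refusers only (section 8) |

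The interviews and record review in section 9 are for participants. A signed records release is an entry criterion (section 7.1), so record access as described covers enrolled people. Refusers supply demographics and reasons for refusal, and they are not called the current practice group.

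**3. Consequence for the estimate.** With n₁ coached and n₂ comparison patients, the standard error of a risk difference is √[p₁(1−p₁)/n₁ + p₂(1−p₂)/n₂]. As described, n₁ = 40 and n₂ = 0, so the second term is undefined. A rank-sum statistic or standardised difference between groups likewise cannot be formed.

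**4. What turns on the missing control rate (all rates assumed; the document gives none).** Take a coached rate p₁ = 0.40, a control rate p₂, two-sided 5% and 80% power. With p̄ = (p₁ + p₂)/2,

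n per arm = [1.960·√(2p̄(1−p̄)) + 0.842·√(p₁(1−p₁) + p₂(1−p₂))]² / (p₁ − p₂)²

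| p₂ | Difference | Numerator | n per arm |
|---|---|---|---|
| 0.10 | 0.30 | (1.200 + 0.483)² = 2.835 | 2.835/0.09 = 31.5 → 32 |
| 0.20 | 0.20 | (1.270 + 0.532)² = 3.249 | 3.249/0.04 = 81.2 → 82 |
| 0.30 | 0.10 | (1.322 + 0.565)² = 3.559 | 3.559/0.01 = 355.9 → 356 |

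The same coached result is compatible with trials that differ in size by 356/32 ≈ 11 times.

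**5. If both groups were meant to sit inside N = 40.** Assume 20 per group and observed 8/20 (40%) against 4/20 (20%). The Wilson limits are 21.9% to 61.3% and 8.1% to 41.6%. The Newcombe 95% interval for the difference is then
- lower: 0.20 − √[(0.400 − 0.219)² + (0.416 − 0.200)²] = −0.082
- upper: 0.20 + √[(0.613 − 0.400)² + (0.200 − 0.081)²] = +0.445

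That is about −8 to +44 points.

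**6. What one cohort can deliver.** The widest exact (Clopper-Pearson) 95% intervals for a proportion are:

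| Denominator | Count | 95% CI | Half-width (points) |
|---|---|---|---|
| 40 | 20 | 33.8% to 66.2% | 16.2 |
| 32 | 16 | 31.9% to 68.1% | 18.1 |
| 24 | 12 | 29.1% to 70.9% | 20.9 |
| 20 | 10 | 27.2% to 72.8% | 22.8 |

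The denominators below 40 are assumed. They can arise because entry requires only a reactive HCV antibody test (section 7.1), and because sustained opioid-treatment linkage is counted after an initial prescription (section 12.1).

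**The case against.** This is a pilot that claims no power for efficacy, limits its secondary comparison to description, and has an acceptability aim for which one arm is a legitimate design. The qualitative analysis is untouched. All of that stands.

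The planned analyses are also not equally blocked. Section 11.2 speaks of reviewing patients' records, at a clinic seeing about 500 people a year, so a record-based comparison of linkage could be set up; on this view it is undefined rather than impossible. Age and gender could be compared with refusers. These points narrow the problem without removing it. Section 11.2 identifies no comparison group, the records release is tied to enrolment, and refusers have no outcome data. Record review would not supply Likert scores either, and people who were never coached cannot rate their satisfaction with coaching.

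A paired before-after Wilcoxon test may have been intended, and within-person changes are estimable. But that is not what a comparison between two groups says, and a change over time is not an effect of coaching against current practice.

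Finally, the sample-size range depends on the assumed rates, and any trial's size is sensitive to its control rate. That is fair: the range shows what is at stake and is not needed to establish the contradiction. One practical point also stands: Table 1 in section 9 lists no satisfaction scale, so even a one-group summary needs the scale and its timing named.

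**Conclusion.** The concern holds. Section 12.3 does not match the study described in the synopsis and sections 4.1.1, 5 and 8, and its between-group outcome analyses cannot be run as written. The effect of coaching relative to current practice, which is what an efficacy trial would need from 12.2, is not identifiable. Proportions under coaching remain estimable, to within about 16 points at worst with all 40 in the denominator.

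This conclusion rests on the text alone. The 11-fold range in future trial size and the −8 to +44 point interval are illustrations on assumed rates and an assumed 20/20 split. The primary acceptability aim survives, so this should be corrected but does not undermine the study. If a non-randomised comparator was intended, selection could bias the difference, depending on how that group is drawn.

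**What to change.** Reconcile 12.2 and 12.3 with section 5 in one of two ways.

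**Option A: keep the single cohort, as section 5 is written.**
- In 12.3, delete the two-group Wilcoxon test and all comparisons with a current practice group.
- Summarise the 5-point Likert satisfaction scores of coached participants by median, interquartile range and full distribution, naming the scale and when it is given.
- Report linkage and retention proportions with exact 95% confidence intervals, and state each denominator.
- In 12.2, replace the effect-size promise with, for example: *No treatment effect will be estimated from this cohort; findings will inform recruitment, retention and, with their confidence intervals, outcome rates under coaching for a future trial.*

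The cost is wording in 12.2 and 12.3, with no change to N. If a satisfaction scale is not already among the interview instruments, it has to be added. The sponsor gives up the effect-size claim and the two-group test.

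**Option B: if a comparison group was intended.**
- Define it in section 5: source, size, eligibility, period, outcome windows, whether it is inside or outside N = 40, whether allocation is randomised, and how its Likert data are obtained.
- Keep the secondary comparison descriptive, as 12.3 already says, and add 95% confidence intervals.
- In 12.2, caveat any use of the difference for planning.

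This costs extra data collection, including Likert responses, and possibly more participants.

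Under either option, the efficacy goal stated in section 3.1 should be aligned with the feasibility and acceptability goal in 4.1 and 12.1. That is an editorial follow-on.
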